5.2 Active Recruitment of Potential Subjects

As discussed above, potential adolescent subjects presenting to clinic sites seeking oral contraception will be informed of the study and invited to participate. If they choose to participate, they will be routed to study staff who will perform the initial screening in person, and conduct the remainder of the enrollment process as described below.

5.3 Study Period

5.3.1 Enrollment Visit, Self-Selection/Purchase Decision

At the enrollment visit, which takes place at the retail pharmacy or health clinic study site and is conducted by trained site staff, initial study inclusion criteria will be reviewed and potential subjects will be shown the Opill® outer package. Subjects will be given as much time as needed to review the information on the outer package. After reviewing the outer package, they will be asked if the product is right for them to use and for those that say the product is right for them, whether they want to purchase/obtain the product for their own use. Reasons for selection/non-selection and purchase/non-purchase will be collected.

5.3.2 Mock Purchase

In many AUTs, subjects are asked to "purchase" the study product, typically for a nominal fee. This purchase transaction is intended to make the study process more OTC-like, and helps minimize the likelihood of subjects enrolling who are not truly interested in the study medication. Subjects do not know at the time of the purchase decision or for the remainder of their study participation that any money that they pay for study product will be reimbursed to them at the end of the study.

In some AUTs, however, the "purchase" is not feasible for one reason or another. In this study, targets for adolescent participation are challenging, requiring the addition of active recruitment in a clinical environment for adolescent subjects only. Barriers to

participation are already quite high for adolescents. Because adolescents seeking care in the clinical environment are typically able to receive their care and medications without any cost to them, subjects enrolled in the clinical environment will not be asked a purchase question. Rather, they will be asked whether they want to receive study product for their own use. There will be no mock purchase transaction. This will eliminate that potential barrier to participation.

Adolescent subjects who respond to study advertising in the traditional way will all be enrolled at pharmacy sites, as will all adult subjects. The mock purchase procedures will be in place for all subjects who enroll at pharmacy sites.

Throughout this document, "purchase" and "purchasers" refers to any subject who either agrees to purchase and conducts a purchase transaction (as will be the case for all adults and any adolescents who enroll at pharmacy sites) or who agrees to be dispensed the study product for their own use (in the case of adolescent subjects enrolled at clinic sites).

5.3.3 After Purchase Decision and Before Study Entry

The purpose of this study is to see how the subject complies with the labeled directions; therefore, the date of the first use of study medication is determined by the subject. Study Day 1 will be defined as the day the product is dispensed to the participant.

On Study Day 1, at the site, subjects will complete the enrollment interview, providing information on any associated medications, associated medical conditions and selected demographic information. Subjects will then be asked to complete the REALM¹ or REALM-Teen² test to establish reading ability.

Next, use phase exclusion criteria will be assessed, and qualified subjects who decide to purchase/obtain the product will provide informed consent. Please note that in this study, as is typical in actual use trials, a waiver of consent will be sought for the prior elements of the enrollment interview, so as to avoid the potential bias to self-selection that the details necessary for informed consent may introduce. The informed consent document will be presented electronically, and signatures will be collected electronically. However, all consent procedures will be conducted face-to-face. There will be no consent administered remotely to subjects (or with parents or legal guardians, if applicable).

Subjects that provide consent will be provided with a self-administered pregnancy test and asked to use it there at the site. Results will be recorded, and any subjects who are found to be pregnant will be excluded from use, and the event documented. Adolescent subjects recruited from the clinical environment whose pregnancy test is positive because of a recent abortion will not be excluded. Subjects who are found to be pregnant based on their initial positive pregnancy test will be asked the self-selection question again to determine if they make a correct non-selection decision once they have the confirmation that they are likely pregnant.

Qualified subjects will be required to provide contact information (for the purposes of conducting telephone follow-up interviews and providing compensation). Subjects who

chose to will then purchase the IP and site study staff will complete the IP accountability form in the EDC system. Subjects will be told they are allowed to return to the study site at any time to purchase/obtain additional study medication. Subjects will subsequently be reimbursed for all purchases, but are not informed of this until the study is completed. Subjects will not be allowed to purchase/obtain more than 8 four-week supply packages during the study period, although this limit will not be communicated to the subjects unless they attempt to purchase/obtain more than that. Any requests for purchase/dispensing of more than the limit will be recorded, as will the reason for such requests.

Subjects will also be informed that interim and end-of-study phone interviews will be conducted at weeks 4, 8, 12, and 16 (with an allowable window of +/- 4 days for interviews at weeks 4 and 8, and +/-5 days for interviews at weeks 12 and 16). Subjects are not required or directed to continue taking the medication for this period. Subjects who have decided to proceed to the use phase of the study will be dispensed the product to use how and when they see fit based only on guidance from labeling.

Subjects will be introduced to and trained to use the online medication use diary. Subjects will also be provided with a subject information card and a self-administered pregnancy test and given instructions to use the test at the end of the study period. Subjects will record the results of the home pregnancy test in the online medication use diary.

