Abbreviations: \rightarrow = ongoing/continuous event; REALM = Rapid Estimate of Adult Literacy in Medicine; REALM-Teen = Rapid Estimate of Adolescent Literacy in Medicine

- a. Day relative to first purchase of study medication (Day 1).
- b. Subjects will be asked to provide a list of any medical conditions they have and any medications they are taking. Females only.
- c. REALM¹ or REALM-Teen² test will be conducted for all subjects regardless of self-selection and purchase decision.
- d. Subjects with a positive pregnancy test at enrollment will be asked to make a selection decision again to better assess self-selection and then will be excluded from the use phase.
- e. Subjects will be allowed to purchase or be dispensed any amount of study medication up to a total of 8 packages at any time during their use phase.
- ^{f.} Early termination interview will be conducted during the study if the subject is discontinued or withdraws consent prior to Week 16.

Glossary and Abbreviations

AAFP American Academy of Family Physicians ACCP American College of Clinical Pharmacy

ACOG The American Congress of Obstetricians and Gynecologists

AΕ Adverse Event

AIDS Acquired Immune Deficiency Syndrome

AMA **American Medical Association**

APHA American Public Health Association

ASRM American Society for Reproductive Medicine

AUT Actual Use Trial

CFR Code of Federal Regulations

CI Confidence Interval

CIL Consumer Information Leaflet

CIOMS Council for International Organizations of Medical Sciences

COC Combined Oral Contraceptive

CRF Case Report Form

CRO Contract Research Organization

Data Collection Instrument DCI

DFL **Drug Facts Label**

DMP Data Management Plan **EDC Electronic Data Capture** EDP

Exposure During Pregnancy

EOS End of Study

Food and Drug Administration FDA

FD&C Food, Drug and Cosmetics (US Federal act)

GCP Good Clinical Practice **HBC** Hormonal Birth Control

HIV Human Immunodeficiency Virus **HPO** Hypothalamic-Pituitary-Ovarian **HRT** Hormone Replacement Therapy

ICH International Council on Harmonization

IEC Independent Ethics Committee IRB Institutional Review Board IΡ Investigational Product IUD Intrauterine Device

LCS Label Comprehension Study

LNG-IUS Levonorgestrel-releasing Intrauterine System MedDRA Medical Dictionary for Regulatory Activities

NHANES National Health and Nutrition Examination Survey OTC Over-the-Counter

PHI Personal Health Information

PII Personally Identifiable Information

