6.4 Pregnancy Testing

During the enrollment interview, after answering the self-selection question, all subjects will be asked if they are currently pregnant, and after informed consent is obtained, subjects will perform a self-administered pregnancy test at the site. Subjects with a positive result will be asked the selection question again, and then excluded from participating in the use phase of the study. Additionally, at the end of the enrollment interview, subjects who are proceeding into the use phase will be provided with a home pregnancy test with the instructions to use it at home at the end of the study and record the results in the online diary. Nurse interviewers will inquire about the results of the home pregnancy test during the EOS interview. After completion of the EOS interview, subjects will be asked to return to the study site to return all unused study medication and packaging. During that visit, an additional pregnancy test will be administered and results entered by site staff. If subjects have not completed the home pregnancy test at the EOS interview, and if they have not returned to the study site for the site-recorded pregnancy test, an additional call will be placed at 5 (+3) days following the EOS interview to collect home pregnancy test results. This will allow for shipping time if the subject requires an additional at home pregnancy test to be sent to them. In addition, at the time a subject withdraws or is withdrawn from the study early, nurse interviewers will inquire if the subject would be willing to take the pregnancy test and report the results in their electronic diary and return to the site for the EOS visit.

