9.3.3.6 Actual Use: Number of pregnancies reported during the course of the study

This endpoint is intended to characterize the pregnancies that may occur during the course of the study. While it does not directly measure behavior related to messages on the DFL, it is of interest. For the purposes of this endpoint, pregnancies will be defined as any reported pregnancy during the use phase of the study, or any confirmed positive pregnancy test (at home or at EOS visit) that is conducted within 12 days of the end of the subject's use phase.

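### Protocol 5.3.3 admits some subjects with a positive enrollment pregnancy test whom 6.4 and schedule footnote d exclude, and endpoint F has no rule for women already positive at entry

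*Protocol*

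**What the plan says.** **Entry rule.** Protocol 5.3.3 first gives a general rule: "any subjects who are found to be pregnant will be excluded from use, and the event documented". It then makes an exception: "Adolescent subjects recruited from the clinical environment whose pregnancy test is positive because of a recent abortion will not be excluded".

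Protocol 6.4 is worded by test result and has no exception: "Subjects with a positive result will be asked the selection question again, and then excluded from participating in the use phase of the study". Footnote d of the Schedule of Activities agrees with 6.4. Its trigger is worded "Subjects with a positive pregnancy test at enrollment will be asked to make a selection decision again". The consequence it gives for the same subjects reads "and then will be excluded from the use phase". Neither refers to 5.3.3. Use phase exclusion 7 in Section 3.3.2 names pregnancy itself rather than a positive test.

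**Counting rule.** For secondary endpoint F, Protocol 9.3.3.6 gives two routes to being counted. The first is a report of pregnancy while the subject is in the use phase. The second rests on testing: "any confirmed positive pregnancy test (at home or at EOS visit) that is conducted within 12 days of the end of the subject's use phase". Section 5.5 asks subjects who leave early to take the end-of-study test as well.

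**SAP.** Section 6.2.2 keeps F as the only secondary endpoint, and Section 6.2.3 keeps adverse events as the only other measure. Section 6.2.4.2 has all reported pregnancies described, with an assessment of whether each arose on or off study drug. It says nothing about a positive test at enrollment.

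**The concern.** There are two linked problems.

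First, a clinic adolescent whose positive test is put down to a recent abortion enters the use phase under 5.3.3 and is excluded under 6.4 and footnote d. Sites working from different pages could treat the same subject differently, and the documents would not show which practice produced the use-phase population.

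Second, once such a subject has been dispensed drug, she has no negative baseline. A positive test at the end of use could be a carried-over result, a pregnancy present at entry, or a conception after entry. Section 9.3.3.6 counts all three alike.

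The second problem bears on what the study still reports. F is one of only two protocol endpoints or measures left in the SAP. Section 7.9 also requires a pregnancy found during treatment to be submitted as a serious adverse event with an exposure-during-pregnancy report, so a misattributed positive could reach the safety tables too.

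**Working it through.** The plan states no figure on this point, so the main check is to compare the passages.

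**Step 1: entry.** Take a clinic-recruited adolescent who consents and tests positive because of a recent abortion.

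| Passage | Trigger | Result for her |
|---|---|---|
| Protocol 5.3.3, general rule | found to be pregnant | not triggered by the test alone |
| Protocol 5.3.3, exception | positive because of recent abortion | stays in |
| Protocol 6.4 | positive result | excluded |
| Schedule footnote d | positive enrollment test | excluded |
| Protocol 3.3.2, exclusion 7 | pregnancy | compatible with 5.3.3 |

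The conflict lies between the 5.3.3 exception and two passages, 6.4 and footnote d. Exclusion 7 is not part of it.

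**Step 2: counting.** Suppose she is dispensed drug and tests positive at the end of use.

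- 9.3.3.6 looks only at use-phase reports and at tests within 12 days of the end of use. The enrollment result plays no part.
- The rule requires a confirmed test but does not define confirmation. In 5.4.4 and 6.8, confirming means that site staff verify the test result. That says nothing about when conception occurred.
- The SAP's on/off-drug assessment has no category for a woman positive at enrollment. An off-drug label could cover conception before dispensing or after stopping.

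**Step 3: when the repeat test falls.** The week 16 contact is day 112 ± 5, so a completer's home test comes at about day 112 − 5 = 107 or later. If the use phase ends at that contact, the counting window closes by day 112 + 5 + 12 = 129. For early leavers, Section 5.5 sets no minimum interval after enrollment. SAP Section 1 says the study was terminated shortly after it began, so early repeat tests are plausible. Whether a carried-over positive would last that long cannot be judged from the documents.

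**Step 4: weight of one case (illustration only).** Assume no true on-study pregnancies and k women counted only because they were positive at entry. The method is the SAP's exact Clopper-Pearson 95% interval: lower limit Beta(0.025; k, n − k + 1), upper limit Beta(0.975; k + 1, n − k). For k = 0 the lower limit is 0. The denominators are the planned 720 users (900 × 0.80) and 140 adolescent users (175 × 0.80, which assumes the same 80% use rate).

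| k | n = 720 | n = 140 |
|---|---|---|
| 0 | 0% (0 to 0.51) | 0% (0 to 2.60) |
| 1 | 0.14% (0.00 to 0.77) | 0.71% (0.02 to 3.92) |
| 3 | 0.42% (0.09 to 1.21) | 2.14% (0.44 to 6.13) |

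The values of k are assumed. The 175 covers pharmacy and clinic adolescents together, while the exception applies only to the latter. The documents do not give the numbers reached before termination; with a smaller denominator, each case weighs more.

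**The case against.** The strongest reply is that 5.3.3 is a specific exception to a general rule and that only a cross-reference is missing. F is a descriptive count with no threshold, and the protocol rules out efficacy conclusions. Every pregnancy will be described individually, the enrollment result is on record, and the exposure report collects an anticipated delivery date. A reader of the case descriptions could pick out a woman who was positive at entry. Protocol edits also cannot change conduct in a study that has stopped.

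Much of this stands. The data largely exist, and no decision turns on a single case. But neither 6.4 nor footnote d points to the exception, and the counting rule as written still includes these women without marking them.

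A reader might also infer stronger points that the documents do not support:

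- *That pharmacy subjects with the same history are excluded under every passage.* They are excluded under 6.4 and footnote d, but exclusion 7 and the general rule in 5.3.3 turn on pregnancy, not on the test.
- *That the self-selection endpoint is distorted.* Sections 8.5.1 and 9.3.1.1.1 re-ask selectors who reported not being pregnant and then test positive, while 5.3.3 re-asks only those found to be pregnant. But 8.5.1 classes anyone who obtains the product as a selector, 8.5.2 makes her incorrect on this ground only if she is pregnant and intends to use while pregnant, and the SAP no longer analyzes self-selection.
- *That F is inflated by some percentage, or that ongoing pregnancies were dispensed drug.* No count or duration supports the first. On the second, the method of attributing a positive test to an abortion is not stated, but Section 3.3.2 requires eligibility to be reviewed and documented before dispensing.

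**Conclusion.** The point holds in two parts. The entry rules contradict each other in current text: 5.3.3 against 6.4 and footnote d. Endpoint F has no rule for a woman dispensed drug after a positive enrollment test, and the SAP's on/off-drug assessment does not supply one.

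The effect is possible miscounting, not demonstrated miscounting. It requires at least one subject admitted under the exception and a later positive test or pregnancy report that meets 9.3.3.6. Neither the number of such subjects nor the persistence of a positive test is documented, so the size is unknown. What raises this above an editorial matter is that F is one of the few outcomes still to be reported.

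**What to change.** 1. Reconcile Protocol 5.3.3, 6.4 and schedule footnote d. Which rule applies, and to which sites, is for the sponsor to decide. Exclusion 7 needs no change. Since the study has stopped, this serves to make clear who could have been dispensed drug and to correct the text before any reuse.
2. In Protocol 9.3.3.6 and SAP 6.2.4.2, flag and list separately any woman dispensed drug with a positive enrollment test, and report F both with and without these women. Describe the timing of conception from the recorded enrollment result and, where available, the anticipated delivery date in the exposure-during-pregnancy report. The SAP sentence is the more immediate change.

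These women should not be dropped from F unless later conception is proved. No pregnancy test is scheduled between enrollment and the end of study, so such proof would often be lacking and a true on-study pregnancy could be lost. Showing both counts avoids that.

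The cost is limited wording changes, one extra listing and a second count. No new data collection is needed.

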5.4 Use Phase

Subjects who enter the use phase of the study take home the IP to use how and when they see fit based only on guidance from the labeling. Contact with subjects during the use phase is limited and targeted toward collecting data necessary to evaluate study endpoints.

5.4.1 Unscheduled Study Site Visits

During any unscheduled visit to a study site for purposes of subjects obtaining additional IP, the study staff contact with the subjects will be limited to:

- 1. Dispensing additional IP with no questions asked, answered, or directions given about the use of the IP by the study staff (except for questions that are explicitly directed to study staff in their capacity as a pharmacist as described above in Section 3.1 above).
- 2. Appropriately documenting the IP dispensed.
- Assisting any subject presenting self-reported AEs by immediately having the subject contact PEGUS Research or by collecting the relevant details and reporting that to PEGUS Research staff.

5.4.2 Online Medication Use Diary

Subjects will be asked to record their use of the IP in an online, web browser-based medication use diary. If a subject does not have easy access to a device with internet connectivity, a device will be provided to them. The diary will record use of the product,

including time of day. Additionally, subjects will be asked to record each instance of heterosexual vaginal intercourse, along with any contraceptive method used.

5.4.3 Telephone Interviews

The four scheduled phone interviews at weeks 4, 8, 12 and 16 will be conducted by PEGUS Research clinical staff (trained nurse interviewers) to collect information such as specific subject behaviors, AEs and concomitant medications.

5.4.3.1 Week 4/8/12/16 Telephone Interview

Trained nurse interviewers will conduct the interim and end of study (EOS) interviews. Interim interviews will be conducted at week 4 (day 28 +/- 4), week 8 (day 56 +/- 4), week 12 (day 84 +/- 5), and week 16 (day 112 +/- 5). The intent of the monthly telephone interview is to collect information about use of the product, AEs and concomitant medications. Each interview will assess whether the subject has started taking the IP, and if so, collect information about how they have taken it. Questions will be designed to collect information about behaviors related to the use of the IP in a non-biasing and masked manner to avoid influencing future behavior (e.g. "Besides taking the medication, is there anything else you have done to prevent pregnancy since we last spoke?").

5.4.3.2 End-of-Study Interview / Early Termination Interview

In most cases, the EOS interview will take place during the week 16 telephone contact, after the week 16 interim interview is complete. However, it is conceptualized as a separate interview in order to allow for collection of key end of study measures in cases where subjects elect to withdraw before the 16-week telephone call. The EOS interview will collect information from the subject regarding the use of other forms of contraception, and the timing of such use. This interview allows for direct questions about the rationale behind any behaviors that are not consistent with the DFL and CIL instructions, without concern about biasing the subject's subsequent behavior. Additional questions will be asked to include subject's experience with the study product, future contraceptive plans, and history and plans for interactions with a healthcare provider. Subjects will also be asked about possible pregnancy and will be asked to take the EOS self-administered pregnancy test, conducted at home, and record the results in their online medication use diary. Electronic reminders to complete and record the results of the self-administered home pregnancy test as well as schedule the EOS visit (described in Section 5.4.4 below) will be delivered every other day beginning at the day following completion of the use phase. Any subjects who do not report the results of their self-administered pregnancy test and also have not completed the end of study visit by 5 days after completion of the use phase will be contacted via telephone and asked to take the provided home pregnancy test and report those results by telephone, and to schedule an EOS visit.

